3.5.2. Variables and time points	19
3.5.3. Approach to analysis	19
3.5.4. Statistical Methods	20
4. Subject Selection and Withdrawal	22
4.1. Inclusion and Exclusion Criteria	22
4.2. Rationale for Using Neonates and Children	22
4.3. Subject Recruitment	23
4.4. Early Withdrawal of Subjects	23
4.4.1. When and How to Withdraw Subjects	23
4.4.2. Data Collection and Follow-up for Withdrawn Subjects	23
5. Safety and Adverse Events	23
5.1. Definitions	23
5.2. Recording of Adverse Events	25
5.3. Reporting of Serious Adverse Events	26
5.3.1. Study Sponsor Notification by Investigator	26
5.4. Dose Escalation Decisions	27
5.5. Stopping Rules	27
5.6. Medical Monitoring	28
5.6.1. Data and Safety Monitoring Board	28
6. Data Handling and Record Keeping	28
6.1. Confidentiality	28
6.2. Source Documents	29
6.3. Case Report Forms	29
6.4. Records Retention	29
7. Study Monitoring, Auditing, and Inspecting	29

- 7.1. Study Monitoring Plan.....29
- 7.2. Auditing and Inspecting.....29
- 8. Ethical Considerations30
- 9. Study Finances.....30
 - 9.1. Funding Source30
 - 9.2. Conflict of Interest.....30
 - 9.3. Subject Stipends or Payments30
- 10. Publication Plan30
- 11. References.....31

- 12. Attachments
 - *Published Manuscript*
 - *Data Safety Monitoring Plan*

List of Abbreviations

CHI:	congenital hyperinsulinism
Ex-9:	Exendin-(9-39)
GLP-1:	glucagon-like peptide-1
GLP-1r:	glucagon-like peptide-1 receptor
K _{ATP} :	ATP- sensitive potassium channel
K _{ATP} HI:	congenital hyperinsulinism due to mutation in the K _{ATP} channel
GIR:	glucose infusion rate

Study Summary

Title	Role of GLP-1 in Congenital Hyperinsulinism: Effect of exendin-(9-39) on glucose requirements to maintain euglycemia
Short Title	Effect of Ex-9 on glucose requirements
Phase	Phase 1/2
Methodology	Open label study
Study Duration	2 years
Study Center(s)	Single-center
Objectives	To examine the effect of exendin-(9-39) on glucose requirements to maintain euglycemia in subjects with congenital hyperinsulinism unresponsive to medical therapy
Number of Subjects	Approximately 30 subjects
Diagnosis and Main Inclusion Criteria	Congenital hyperinsulinism Main inclusion criteria: unresponsive to medical therapy with diazoxide
Study Product, Dose, Route, Regimen, Duration of administration	Exendin (9-39) 1000-30000 pmol/kg/min (0.2-6 mg/kg/hr) intravenous infusion over 9 hours.
Reference therapy	Effect will be evaluated compared to vehicle (normal saline) baseline
Statistical Methodology	Average glucose infusion rate during the last 2 hours of exendin-(9-39) infusion will be compared to glucose infusion rate during the last 2 hours of vehicle infusion. Standard t-test, $p < 0.05$

Schedule of Events

STUDY DAYS 1 & 2*

Procedures	Day 0 (regardless of group assignment)	Vehicle infusion day	Exendin – (9-39) infusion day
Hypersensitivity test ¹ chemistry profile, electrocardiogram, CBC, urinalysis ²	x		
Heart rate, blood pressure, respiratory rate, temperature		x	x
Maintain blood glucose >70mg/dL - dextrose infusion rate will be adjusted to maintain glucose in the range of 70-90mg/dL ³		x	x
Infuse Saline (vehicle) for 9 hours		x	
Infuse exendin-(9-39) for 9 hours			x
Blood glucose will be checked every 30min by heel stick during study period		x	x
Betahydroxybutyrate will be checked every hour by heel stick during the study period		x	x
Plasma levels of exendin-(9-39) 1hr, 5hr, 9hr during study period and, 1hr, 3hr and after infusion is discontinued			x
Plasma glucose and plasma insulin will be measured at 0, 1, 5, and 9 hours		x	x

¹ Test of immediate hypersensitivity may be done the day prior or the morning of the study prior to the start of the infusion.

² Chemistry profile, CBC, and urinalysis will be repeated at end of study.

³ Blood glucose will be checked every 30 minutes by heel stick during study period

*Day 1 and 2 crossover randomized design

Schedule of Blood Drawing

Study Day 1 & 2: (crossover randomized design)

Total blood volume for Day 1 is 9.4 mL about 2 teaspoons

Total blood volume for Day 2 is 18.2 mL about 3 2/3 teaspoons

Total blood volume for safety laboratories before and after the study is 10 mL

Blood test	Time points				Post infusion	
	0hr	1hr	5hr	9hr	10hr	12hr
Blood Glucose ¹	X	X	X	X	X	X
Betahydroxybutyrate ²	X	X	X	X	X	X
Plasma glucose and plasma insulin	X	X	X	X		X ³
Plasma levels of exendin- (9-39) (study drug day only)		X	X	X	X	X

¹ Blood glucose will be checked every 30 minutes by heelstick. Subjects who have discontinued the dextrose infusion at hour 9 during the exendin-(9-39) infusion will continue to have glucose levels checked every 30 minutes up to hour 12 or until blood glucose < 70 mg/dL, whichever comes first

² Betahydroxybutyrate will be checked hourly by heel stick. Subjects who have discontinued the dextrose infusion at hour 9 during the exendin-(9-39) infusion will continue to have betahydroxybutyrate checked every hour up to hour 12 or until blood glucose < 70 mg/dL, whichever comes first

³ Subjects who have discontinued the dextrose infusion at hour 9 during the exendin-(9-39) infusion will have plasma glucose and plasma insulin levels checked either at hour 12 or when blood glucose < 70 mg/dL, whichever comes first

Role of GLP-1 in Congenital Hyperinsulinism

1. Introduction

This document is a protocol for a human research study. This study is to be conducted according to US and international standards of Good Clinical Practice (FDA Title 21 part 312 and International Conference on Harmonization guidelines), applicable government regulations and Institutional research policies and procedures.

1.1. *Background Information and Rationale*

1.1.1. *Congenital Hyperinsulinism*

In infants and children, as in adults, the most common cause of hypoglycemia is hyperinsulinism (HI). However, unlike adults, HI in children most often represents a genetic disorder of insulin regulation rather than an acquired islet tumor (1). Congenital HI (CHI) is a genetic disorder of pancreatic β -cell function characterized by failure to suppress insulin secretion in the presence of hypoglycemia, resulting in brain damage or death if inadequately treated. The estimated incidence of CHI in this country is 1:20,000 to 1:50,000. Mutations in nine genes have been associated with CHI: *ABCC8*, the gene encoding the sulfanylurea receptor-1 (SUR-1) (2); *KCNJ11*, the gene encoding the inward rectifying potassium channel (Kir6.2) (3; 4); glucokinase (*GCK*) (5); glutamate dehydrogenase (*GLUD-1*) (6); *HADHSC* encoding the mitochondrial enzyme short-chain 3-hydroxyacyl-CoA dehydrogenase (SCHAD) (7); and *SCL16A1*, which encodes the monocarboxylate transporter 1 (MCT1) (8); *HNF1A*, the gene encoding hepatocyte nuclear factor 1 alpha (9); and *UCP2*, encoding uncoupling protein 2 (10). Hyperinsulinism can also be associated with Beckwith Wiedemann syndrome, which results from various genetic or epigenetic anomalies in the highly imprinted region of chromosome 11p15.5 (11). Loss-of-function mutations in the K_{ATP} channel (composed of two subunits: Kir6.2 and SUR-1) are responsible for the most common and severe form of HI ($K_{ATP}HI$), with most patients requiring near-total pancreatectomy to control hypoglycemia, leading to prolonged hospitalization and life threatening complications (1). Overall, inactivating K_{ATP} channel mutations are found in 90% of cases that require surgery. In 9% of these cases a mutation is not identified (12).

The K_{ATP} -sensitive channels couple the metabolic state of the β -cell to membrane potential by responding to changes in intracellular ATP concentration. In pancreatic β -cells, closure of the channel by the elevation of ATP/ADP ratio following stimulation with glucose leads to depolarization of the membrane and activation of a voltage-dependent calcium channel that ultimately results in exocytosis of insulin-containing granules (13). Diazoxide, the mainstay of medical therapy for hyperinsulinism, suppresses insulin by promoting the opening of the β -cell K_{ATP} channels; therefore it is ineffective in patients with $K_{ATP}HI$. The second line of medical therapy for hyperinsulinism is octreotide, a somatostatin analog.

The initial response to octreotide is good in most infants with hyperinsulinism but tachyphylaxis develops after a few doses, rendering therapy inadequate for long-term use in most cases (14). Calcium channel blockers have also been tried unsuccessfully (15). Thus, most of these patients require surgical palliation by near-total pancreatectomy, which is not curative but carries a high risk of either persistent hypoglycemia or insulin-requiring diabetes (1).

We have now proof-of-concept data in both animal models (16) and in affected patients (17) indicating that exendin-(9-39) is a promising potential therapy for infants with CHI that cannot be treated with currently-available medications (see preliminary results). In an animal model of K_{ATP} Hyperinsulinism (*SUR-1^{-/-}* mouse), a continuous infusion of exendin-(9-39) corrected the fasting hypoglycemia by inhibiting insulin secretion. Furthermore, in islets isolated from these mice, exendin-(9-39) did not only inhibit baseline insulin secretion but also blocked amino acid-stimulated insulin secretion (16), suggesting that this peptide may correct both fasting hypoglycemia and protein-induced hypoglycemia in affected human subjects.

1.1.2. Clinical Phenotype of K_{ATP} Hyperinsulinism

$K_{ATP}HI$ is characterized by large for gestational age birth weight (due to stimulation of fetal growth by excessive insulin *in utero*), neonatal onset of hypoglycemia, and unresponsiveness to diazoxide therapy. In addition to fasting hypoglycemia, children with $K_{ATP}HI$ have protein-induced hypoglycemia (18). Most reported K_{ATP} channel mutations are recessive, however a few dominantly expressed mutations have been reported (19-21). The dominant defects retain responsiveness to diazoxide and tend to be milder.

There are at least two distinct histological forms of $K_{ATP}HI$, diffuse hyperinsulinism and focal hyperinsulinism. In focal hyperinsulinism (approximately 40-60% of all cases) a somatic reduction to homozygosity (or hemizygosity) of a paternally inherited mutation of *ABCC8* or *KCNJ11* and a specific loss of maternal alleles of the imprinted chromosome 11p15 region result in a focal lesion. Pre-operative identification and localization of these focal lesions by ¹⁸F-fluoro-L-DOPA facilitates local resection of the lesion and cure of this form of hyperinsulinism (22-24). Infants with diffuse hyperinsulinism require a near-total pancreatectomy (98%) to control the hypoglycemia and often require additional therapy with octreotide, and/or frequent feedings to maintain euglycemia. At The Children's Hospital of Philadelphia's Congenital Hyperinsulinism Center, the largest center in this country caring for children with disorders of insulin regulation, we evaluate and treat approximately 20-30 infants with medically-unresponsive hyperinsulinism requiring pancreatectomy every year. Among cases with diffuse hyperinsulinism, approximately 54% had persistent hypoglycemia after a near-total pancreatectomy, up to 24% required a second pancreatectomy for persistent hypoglycemia, 18% had persistent hypoglycemia but were medically controlled, and 20% had insulin-requiring diabetes. Thirty-one percent of the cases had surgical complications, including bowel obstruction, pancreatic exocrine insufficiency, necrotizing enterocolitis and death (1 from necrotizing enterocolitis and 1 from bowel obstruction).

1.1.3. Metabolism and Insulin Secretion in Islets Lacking K_{ATP} Channels

Animal models have been generated to replicate the defect in human K_{ATP}HI. Mice lacking Kir6.2-containing K_{ATP} channels (*Kir6.2*^{-/-} mice) show transient hypoglycemia as neonates. With age the *Kir6.2*^{-/-} mice develop fasting hyperglycemia and glucose intolerance (25). SUR-1 knockout (*SUR1*^{-/-}) mice have also been generated (26). *SUR1*^{-/-} mice are both significantly more hyperglycemic when glucose-loaded and significantly more hypoglycemic when fasted than the control animals (27). Despite their impaired response to glucose, *SUR1*^{-/-} mice secrete normal amounts of insulin after a meal, through intact second phase insulin secretion (28).

Isolated islets from *SUR1*^{-/-} mice, exhibit all the features expected to result from nonfunctional K_{ATP} channels, including β-cell depolarization and elevation of intracellular calcium (28; 29). *SUR1*^{-/-} rodent islets exhibit an abnormal pattern of basal and fuel-stimulated insulin secretion. Basal insulin secretion is two-three fold higher in *SUR1*^{-/-} islets compared to wild type controls (30; 31). Although the pattern of glucose-stimulated insulin secretion in these islets has been an issue of controversy, in all but one study (32) the response to high glucose was virtually absent or small compared to control islets (28-30; 33; 34). Stimulation by acetylcholine and GLP-1 have been shown to increase glucose responsiveness in these islets (34). In contrast to the poor response to glucose, isolated *SUR1*^{-/-} islets are hypersensitive to amino acids. After stimulation with an amino acid mixture, insulin release increases by 3-fold in *SUR1*^{-/-} islets, while normal islets are not affected by this stimulus, unless depolarized with glucose or sulfonylureas (30). These findings are congruent with the clinical observation of protein sensitivity in K_{ATP}HI (35). Evidence from *SUR1*^{-/-} islets (36) and *Kir6.2*^{-/-} (37) and *SUR1*^{-/-} (38) mice demonstrating impaired glucagon secretion implicates K_{ATP} channels as regulators of glucagon secretion. The role of K_{ATP} channels in glucagon secretion seems to be independent of insulin and directly regulated by alpha cells K_{ATP} channels (39).

Isolated islets from human subjects with K_{ATP} hyperinsulinism have also been studied but in a more limited way. Electrophysiological studies of islets from infants with HI show an absence of K_{ATP} channel activity and constitutively elevated intracellular calcium. Basal insulin secretion from these islets was 10-fold higher than controls. In static incubations, glucose caused release of insulin in a dose-dependent manner and acetylcholine, ATP and UTP also increased insulin secretion (40).

1.1.4. Glucagon-like Peptide-1 Receptor Agonists and Antagonists

Glucagon-like peptide-1 (GLP-1) is an incretin hormone secreted by enteroendocrine L-cells in response to ingested nutrients. GLP-1 was first reported in 1987 to be a potent stimulator of glucose-dependent insulin release (41). Since then, numerous studies using GLP-1 agonists, antagonists, as well as genetic loss-of and gain-of-function rodent models have demonstrated that GLP-1 not only enhances postprandial insulin secretion (42-44) but has other actions that are complementary to the incretin effect, including inhibition of glucagon

secretion (45; 46), hepatic glucose production (47; 48), gastric emptying (49; 50), and appetite (51; 52).

The major physiological stimulus to L-cells is nutrient ingestion, with circulating levels of GLP-1 rising by two- to threefold in response to a mixed meal in humans (53). The regulation of GLP-1 secretion by ingested nutrients is complex and thought to involve indirect vagal pathways as well as direct luminal stimulation of the intestinal L-cells (54). Studies in a GLP-1-secreting cell line (GLUTag) have demonstrated that glucose and other metabolized sugars enter the L-cells (likely via a glucose transporter, GLUT-1 or GLUT-5) and induce depolarization by closure of K_{ATP} channels (Kir6.2/SUR-1) (55; 56). A rise in cytoplasmic Ca^{2+} concentration due to opening of voltage gated calcium channels is part of the secretion mechanism (57). A different mechanism involving electrogenic substrate entry to the cell through sodium-glucose transporters results in K_{ATP} channel independent glucose-stimulation of GLP-1 release (58). Given the common embryological origin of the pancreas and intestine it is not surprising that the enteroendocrine cells and β -cells share similar mechanisms of glucose sensing and response; furthermore, glucokinase, the “glucose-sensor” in β -cells, is also expressed in these cells (59). GLP-1 secretion has not been studied in $K_{ATP}HI$, but the observed similarities between pancreatic β -cells and enteroendocrine L-cells suggest that glucose-stimulated GLP-1 secretion may be affected in subjects with $K_{ATP}HI$. Furthermore, our islet studies suggest that the GLP-1r is constitutively active in *SUR-1*^{-/-} islets (16).

A single GLP-1 receptor (GLP-1r) has been identified and is expressed in the pancreatic islet, the gastrointestinal mucosa, heart, lung, kidney, and the brain (60). A mouse with a targeted gene deletion of the GLP-1r has been shown to have fasting hyperglycemia and glucose intolerance, but no apparent major abnormalities in the function of the lungs, GI tract or CNS (61-63). Studies in cell lines or transfected cells have demonstrated that GLP-1 binds to the GLP-1r and activates intracellular signaling in great part through activation of adenylyl cyclase and the generation of cAMP (64; 65).

The exendin peptides, exendin-3 and exendin-4, were originally isolated from the saliva of the Gila Monster, *Heloderma horridum*, using an assay for N-terminus Histidine residues (66-69). Exendin-3 interacts with the VIP receptor, but exendin-4 is a high affinity agonist of the GLP-1r. Exendin-4 is bound more avidly than GLP-1 (70), and is relatively more potent than GLP-1 in stimulating insulin secretion (71; 72). In addition, because it is not susceptible to metabolism by dipeptidyl-peptidase IV, exendin-4 has a longer circulating half-life than GLP-1 (73; 74). Exendin-4 (Exenatide, Byetta®), is approved for the treatment of type 2 diabetes mellitus, and other GLP-1 analogues are currently in late phase of clinical development (60). A truncated form of exendin-4, exendin-(9-39), has been shown to be a specific antagonist of the GLP-1r *in vitro* (71; 75) and *in vivo* in a variety of animal models (76-78) and in humans (79). We have shown that antagonism of the GLP-1r by exendin-(9-39) results in a persistent elevation of fasting blood glucose levels in normal mice (80).

In human subjects, Schirra and colleagues used exendin-(9-39) during glucose clamps, with and without concurrent infusions of GLP-1 (79). At a dose of 300 pmol/kg/min (0.06 mg/kg/hr), exendin-(9-39) blocked GLP-1 induced insulin secretion by 85-95%. In addition, administration of exendin-(9-39) increased plasma glucagon concentrations, indicating the importance of GLP-1 in the regulation of the islet α -cell. Edwards et al. also infused exendin-(9-39) into healthy volunteers (81). In this study subjects were given doses of 5-500 pmol/kg/min (0.001-0.1 mg/kg/hr) during infusion of 0.5 pmol/kg/min of GLP-1. Significant antagonism of GLP-1-induced insulin secretion, a 21% decrease, was noted with 50 pmol/kg/min (0.01 mg/kg/hr) of exendin-(9-39), and 500 pmol/kg/min (0.1 mg/kg/hr) completely abolished the effect of exogenous GLP-1. Furthermore, administration of exendin-(9-39) to fasted subjects resulted in increased plasma fasting glucose levels. These investigators also studied the effect of exendin-(9-39) on endogenous GLP-1-stimulation of insulin secretion by infusing 500 pmol/kg/min (0.1 mg/kg/hr) during oral glucose tolerance tests. In this experiment exendin-(9-39) caused glucose intolerance relative to a control infusion of saline. The circulating half-life of exendin-(9-39) was determined to be ~ 30 minutes using a specific radioimmunoassay. Interestingly, in both studies the relative concentrations of exendin-(9-39) necessary to completely block GLP-1 were ~ 1:1000, higher than would have been predicted by the relative binding of these two peptides determined *in vitro* (68; 70; 71). These studies demonstrate that exendin-(9-39) acts as a GLP-1r antagonist in humans, and that GLP-1 has a physiologic role in glucose metabolism in healthy subjects.

1.1.5. Significance

Congenital hyperinsulinism is a devastating disease affecting approximately 100 to 200 neonates each year in the USA. The lack of effective medical therapies results in the need for a near total pancreatectomy to ameliorate the hypoglycemia. This surgical approach carries a high risk of complications such as diabetes, bowel obstruction, malabsorption, necrotizing enterocolitis and death. Furthermore, a significant number of the infants continue to have hypoglycemia after the surgery requiring continuous administration of glucose by a gastrostomy tube to maintain euglycemia. Despite the impressive recent advances in the understanding of the molecular biology of congenital hyperinsulinism, there have not been any advances in terms of medical therapies for over 20 years. As shown in the Preliminary Studies section, we have data showing very promising effects of antagonism of the GLP-1 receptor by exendin-(9-39) not only in a mouse model but also in human subjects with hyperinsulinism due to K_{ATP} channel mutations. The development of this peptide as a therapeutic agent for this disorder would represent a major advance in the field.

1.2. Name and Description of Investigational Product

The principal investigator holds an investigational new drug application for the use of exendin-(9-39) in this population (IND#76,612). This protocol is being added to the original application.

1.2.1. Exendin-(9-39)

Exendin-(9-39), a truncated form of exendin-4 (exenatide, Byetta[®], FDA approved for the treatment of type 2 diabetes mellitus), is a specific antagonist of the GLP-1r with opposite effects on glucose levels than the agonist, exendin-4. In human studies, exendin-(9-39) has been shown to increase fasting plasma glucose levels (81). No side effects, including no effects on blood pressure and heart rate, have been reported with the use of this peptide in normal human subjects (79; 81). Similarly, the peptide has appeared to be well-tolerated in our pilot studies as well (see below). There is limited data on the pharmacokinetics of exendin-(9-39) in human subjects. The circulating half-life of exendin-(9-39) was determined to be ~ 30 minutes using a specific radioimmunoassay (81), but no data on the metabolism of the peptide is available. It is expected that the metabolism of exendin-(9-39) will be similar to the metabolism of the parent peptide, exendin-4 (Exenatide-Byetta[®], Amylin Pharmaceuticals, Inc.) from which it differs by only eight amino acids. The intravenous half-life of both peptides is very similar. Non-clinical studies have shown that exenatide is predominantly eliminated by glomerular filtration with subsequent proteolytic degradation. The mean apparent clearance of exenatide in humans is 9.1 L/h and the mean terminal half-life is 2.4 h. These pharmacokinetic characteristics of exenatide are independent of the dose. In patients with mild to moderate renal impairment (creatinine clearance 30 to 80 mL/min), exenatide clearance was only mildly reduced (Product insert, Amylin Pharmaceuticals, Inc.).

1.2.2. Chemistry, manufacturing, control

For our studies, exendin-(9-39) was synthesized by American Peptide Company (Corporate Offices, [name]) under cGMP guidelines. The peptide was purified to $\geq 99\%$ by HPLC, and the sequence and mass verified (by Mscan and mass spectral analysis). The investigational drug was formulated by the University of Iowa Pharmaceuticals ([name], a GMP facility) in a 10mM Citrate Buffer, pH 6.0 (Citric Acid Monohydrate USP, Sodium Citrate Dihydrate USP, and d-Mannitol, USP) and stored in sterile 5 mL vials with stopper and seal (West Pharmaceutical) in lyophilized form at -20° C. Each vial contains 25 mg of exendin-(9-39). For administration, the Investigational Pharmacy at the Children's Hospital of Philadelphia will dilute the peptide in 0.9% NaCl and 0.25% human serum albumin to a final concentration of 0.1mg/mL. The 25% human serum albumin will be obtained from Grifols or Octapharma (based on availability).

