2.1. Specific Aim

To examine the effect of exendin-(9-39) on glucose requirements to maintain euglycemia in infants with congenital hyperinsulinism unresponsive to medical therapy.

Secondary Aim. To determine therapeutic plasma levels, plasma half-life and pharmacokinetics of exendin-(9-39) during an intravenous infusion.

Hypothesis: *In infants with hyperinsulinism unresponsive to medical therapy, antagonism of the GLP-1 receptor by exendin-(9-39) will result in decreased glucose requirements to maintain euglycemia, as a result of suppressed insulin and increased glucagon secretion.*

Rationale: Infants with congenital hyperinsulinism present with severe hypoglycemia shortly after birth. Approximately 50% of these infants are unresponsive to available medical therapy (diazoxide and octreotide) and require a pancreatectomy to ameliorate the hypoglycemia. Before surgery, the maintenance of euglycemia is dependent on high glucose infusion rates (up to 20-25 mg/Kg/min) by intravenous or central lines. This practice is frequently associated with severe complications including sepsis and fluid overload which in the presence of the characteristic myocardial hypertrophy seen in these patients puts them at high risk for heart failure. Based on published studies demonstrating that exendin-(9-39) reduces the glucose infusion rates required to maintain blood glucose levels at a target level in normal human subjects (79) and our preliminary data demonstrating the insulin suppressant effects of exendin-(9-39) in subjects with hyperinsulinism, we propose that by continuously infusing exendin-(9-39) we will be able to reduce the glucose infusion rates needed to maintain euglycemia in infants with congenital hyperinsulinism.

Primary outcome variable: glucose infusion rate during the last 2 hrs of infusion of exendin-(9-39).

Secondary outcome variables: plasma glucose 1 hr after initiation of infusion, insulin, and betahydroxybutyrate levels measured at different intervals during the study. Exendin-(9-39) plasma levels.

Safety variables: Primary safety endpoints will include all types of adverse experiences, in addition to laboratory safety tests (hematology, chemistry, and urinalysis). 12-lead electrocardiograms (ECGs), vital signs and physical examinations will also be recorded.

3. Study Design

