6. Feedings: Infants will be allowed to continue feedings by mouth or by nasogastric/gastrostomy tube. Feedings will be continued every 3 hours and the volumes offered will be maintained equal during the two 9 hr study

- periods. The volume taken with each feeding will be recorded. Only intravenous glucose will be adjusted to maintain euglycemia.
7. Randomization: The investigational drug services will assign the order of the studies by randomization. They will inform the PI, study coordinator, and CTSC.
 8. Intravenous infusion of exendin-(9-39) and vehicle. All subjects will receive an infusion of exendin-(9-39) and vehicle for 9 hours on two separate days and in random order. Exendin-(9-39) /vehicle will be infused intravenously over a period of 9 hours starting at approximately the same time \pm 90 minutes on each day. The starting dose of exendin-(9-39) will be 1000 pmol/kg/min (0.2 mg/kg/hr). The dose will be escalated as outlined below. The volume of saline to be infused will be calculated to match the volume rate of exendin-(9-39).
 9. Post-infusion follow-up for subjects who have been able to discontinue dextrose infusion. Subjects who have been able to discontinue the dextrose infusion and who are not on supplemental dextrose infusion at the end of the study will continue to be monitored without additional dextrose infusion for up to 3 hours after the end of the study drug infusion, or until blood glucose is $<$ 70 mg/dL (whichever comes first). In addition to blood glucose monitoring every 30 minutes and betahydroxybutyrate every 1 hr from a capillary sample, a venous sample will be drawn at the end of 3 hours (or when blood glucose $<$ 70 mg/dL, whichever comes first) for plasma insulin and glucose.
 10. Dose schemes.

Scheme #1 (completed as of date of Protocol Amendment 7): exendin-(9-39) infused for 12 hrs at a dose of 100 pmol/kg/min (0.02 mg/kg/hr).

Scheme #2 (completed as of date of Protocol Amendment 7): exendin-(9-39) infused for 12 hrs at a dose of 200 pmol/kg/min (0.04 mg/kg/hr).

Scheme #3 (completed as of date of Protocol Amendment 7): exendin-(9-39) infused for 6 hrs at a dose of 500 pmol/kg/min (0.1 mg/kg/hr).

Scheme #4 (new as of date of Protocol Amendment 7): Dose escalation will be done as described below:

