 - a. Cohorts 1-2: at least 3 and up to 6 subjects per cohort, will be included in each of the first two cohorts. In any of the first 2 cohorts, if discontinuation of intravenous dextrose is achieved in 2 out of the 3 subjects up to three additional patients (at least 2 with diffuse disease, as defined by PET scan and/or genetics) may be enrolled in order to meet the Success Stopping Criteria (see 11a below).
 - b. Cohorts 3- 4: four subjects, with at least 2 subjects with diffuse disease. If discontinuation of intravenous dextrose is achieved in 1 or 2 of the 4 subjects, an additional subject with diffuse may be enrolled in order to meet the Success Stopping Criteria (see 11a below).

- c. The dose will be increased in $\frac{1}{2}$ log increments between cohorts as specified below:

Group	Dose Scheme (mg/kg/hr for 9 hours)	Total Dose (mg/kg)	Number of Subjects
1	0.2	1.8	3-6
2	0.6	5.4	3-6
3	2	18	3-5
4	6	54	4-6

11. Stopping Criteria:

- a. Success Stopping Criteria: the dose escalation will be stopped if in a cohort at least 2 subjects with diffuse disease are able to have dextrose infusion discontinued for the final 2 hours of the study period.
- b. Safety Stopping Criteria: if an exaggerated pharmacology effect is observed (blood glucose greater than 200 mg/dL for 2 hours off dextrose infusion) dose escalation will be stopped and the dosing algorithm will be modified to proceed with a dose that is 2 fold higher the previous level observed to be safe. Dosing will be stopped if any severe adverse event is observed.

12. Calculation of glucose infusion rate. Glucose infusion rate over the last 2 hours of the treatment period will be calculated by adding the total amount of intravenous glucose (in mg) received over 2 hours divided by the weight in Kg and by time (120 min).

13. Determination of therapeutic plasma levels, plasma half-life and pharmacokinetics of exendin-(9-39). During the infusion with exendin-(9-39) blood samples will be obtained at 1, 5, and 9 hours, and at 1 and 3 hours after the infusion ends. Should there be difficulty in establishing blood drawing lines to obtain samples of the secondary outcome variables the study will proceed with collection of the primary outcome variable only (glucose infusion rate). Plasma levels of exendin-(9-39) will be determined by mass spectrometry.

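### The only infusate strength the protocol states, 0.1 mg/mL, implies 20 and 60 mL/kg/hr at the cohort 3 and 4 doses, which is not plausible for infants

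*Combined protocol and SAP*

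**What the plan says.** Section 1.2.2 (Chemistry, manufacturing, control) describes one preparation for administration: the investigational pharmacy "will dilute the peptide in 0.9% NaCl and 0.25% human serum albumin to a final concentration of 0.1mg/mL". It gives no range, no alternative for higher doses and no maximum volume. The only other strength in the protocol is for the intradermal hypersensitivity test (section 3.4, item 1), which is not the treatment infusion.

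The Study Summary gives the regimen as "Exendin (9-39) 1000-30000 pmol/kg/min (0.2-6 mg/kg/hr) intravenous infusion over 9 hours". The dose table in section 3.4, item 10c sets four levels: 0.2, 0.6, 2 and 6 mg/kg/hr, each for 9 hours. Under item 8, the saline volume on the vehicle day follows the drug-day volume rate. Intravenous dextrose is titrated on both days (item 5), and feeds go on: "Infants will be allowed to continue feedings by mouth or by nasogastric/gastrostomy tube" (item 6).

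The rationale in section 2.1 says that high-rate glucose infusion in these infants brings "severe complications including sepsis and fluid overload", and that with their myocardial hypertrophy this "puts them at high risk for heart failure".

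**The concern.** Dose and strength together determine volume. A strength that suits the low doses becomes unworkable as the dose rises 30-fold from 0.2 to 6 mg/kg/hr, unless the strength rises too. The written plan raises only the dose.

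If escalation reaches cohort 3, the preparation as written could not credibly or safely be given on either study day. Staff would then have to use a strength the protocol does not describe, or delay the cohort. Cohorts 3 and 4 are conditional but are a realistic prospect. Item 11a says "the dose escalation will be stopped if in a cohort at least 2 subjects with diffuse disease" come off dextrose for the final 2 hours, which is a demanding condition for stopping early. Section 1.4 also reports no effect on glucose infusion rate in two neonates at 0.1 mg/kg/hr.

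**Working it through.** **Inputs**

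- Strength: 0.1 mg/mL in 0.9% NaCl with 0.25% albumin (section 1.2.2).
- Dose rates: 0.2, 0.6, 2 and 6 mg/kg/hr for 9 hours (section 3.4, item 10c).
- Illustrative weight: 5 kg, the paediatric median in the pharmacokinetic model (section 1.4).
- Mean baseline glucose infusion rate: 13.2 mg/kg/min (section 3.5).

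**Step 1: reproduce the plan's own figures.** Total dose = rate × 9 h: 0.2 × 9 = 1.8; 0.6 × 9 = 5.4; 2 × 9 = 18; 6 × 9 = 54 mg/kg. All four match the dose table. The protocol states no infusion volumes, so there is nothing to reproduce for those.

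**Step 2: volume.** Volume rate = dose rate / 0.1 mg/mL. Total volume = volume rate × 9 h.

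| Cohort | Dose (mg/kg/hr) | Volume rate (mL/kg/hr) | Volume over 9 h (mL/kg) | For 5 kg |
|---|---|---|---|---|
| 1 | 0.2 | 2 | 18 | 0.09 L |
| 2 | 0.6 | 6 | 54 | 0.27 L |
| 3 | 2 | 20 | 180 | 0.9 L |
| 4 | 6 | 60 | 540 | 2.7 L |

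**Step 3: sodium and albumin on the drug day.**

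- NaCl at 0.009 g/mL: cohort 3, 180 × 0.009 = 1.62 g/kg; cohort 4, 540 × 0.009 = 4.86 g/kg.
- Sodium (NaCl 58.44 g/mol): 1.62 / 58.44 = 27.7 mmol/kg; 4.86 / 58.44 = 83.2 mmol/kg. Sodium from the citrate buffer and the albumin stock is not counted.
- Albumin at 0.0025 g/mL: 180 × 0.0025 = 0.45 g/kg; 540 × 0.0025 = 1.35 g/kg.

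Volume-matched saline gives the same NaCl load again on the vehicle day.

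**Step 4: comparison with the fluid load the protocol already warns about.** Section 2.1 describes glucose infusion rates up to 20-25 mg/kg/min. At 25 mg/kg/min the infant receives 25 × 60 = 1,500 mg/kg/hr, which takes 15 mL/kg/hr as 10% dextrose or 7.5 mL/kg/hr as 20% dextrose (strengths assumed). Cohort 3's study infusate alone exceeds both, and cohort 4's is 4 to 8 times as much. At the mean baseline rate, 13.2 × 60 = 792 mg/kg/hr takes 7.9 mL/kg/hr (10%) or 4.0 mL/kg/hr (20%). The study infusate would be added to this.

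**Step 5: strengths that would work.** Strength = dose rate / target volume rate.

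- To hold cohort 1's 2 mL/kg/hr: 2 / 2 = 1 mg/mL for cohort 3; 6 / 2 = 3 mg/mL for cohort 4.
- To stay within cohort 2's 6 mL/kg/hr: 2 / 6 = 0.33 mg/mL; 6 / 6 = 1 mg/mL.

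The completed schemes (0.02 to 0.1 mg/kg/hr) needed only 0.2 to 1 mL/kg/hr at 0.1 mg/mL. The figure may have been carried over from them, but the protocol does not say so.

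**The case against.** The arithmetic is not in dispute, but several points can be made for the plan.

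- **Wording.** Section 1.2.2 is a manufacturing paragraph and does not say that the strength applies to all doses. Section 3.4, item 8 gives the dose in mg/kg/hr without a concentration, and its volume matching works at any strength. It is fair that applying 0.1 mg/mL to every cohort is a reading, but it is the only strength the protocol offers.
- **Other files.** The IND manufacturing section or the pharmacy records may specify a higher strength. They are not available here, so the finding covers the protocol text only.
- **No stated limit.** No two statements contradict each other, and nothing in the protocol marks 6 mL/kg/hr as acceptable and 20 as not. That stands. The warning in section 2.1 concerns glucose infusion, and applying it to study infusate is an extension.
- **Oversight.** Escalation is reviewed by the investigator, the Safety Officer and the pharmacologist (section 5.4), vital signs are taken hourly, severe cardiac failure is excluded, and blood pressure or pulse instability can stop treatment. None of these limits volume before dosing, and cohort 2 data at 6 mL/kg/hr would not show a problem at 20.
- **Consequence.** The pharmacy would probably notice. That is likely, but it is not a written safeguard, and acting on it would mean departing from the stated preparation.

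**Conclusion.** The concern holds, and the text must be corrected before cohort 3. As written, two of the four planned dose levels call for 20 and 60 mL/kg/hr, which is 180 and 540 mL/kg over 9 hours on each study day. The volumes follow exactly from the stated strength and doses. That they cannot be delivered safely is a clinical judgement: hard to contest at cohort 4, and well supported at cohort 3 given the added dextrose and feeds and the vulnerability to fluid overload that the protocol itself describes. The conclusion assumes that 0.1 mg/mL applies to all cohorts, since no alternative is given. It matters only if escalation goes past cohort 2. Cohort 1, at 2 mL/kg/hr, works as written.

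**What to change.** Replace the single 0.1 mg/mL in section 1.2.2 with a final strength, or a permitted range, for the higher-dose cohorts. Strengths of 1 mg/mL (cohort 3) and 3 mg/mL (cohort 4) would hold 2 mL/kg/hr; at least 0.33 and 1 mg/mL would stay within 6 mL/kg/hr. The sponsor and pharmacy should choose the values and confirm stability and compatibility, for which the protocol gives no data at these strengths. Vials contain 25 mg and are 5 mL in size, so vial size does not appear to rule these strengths out. Set the matched saline volume from the new strengths. Optionally, add a mL/kg/hr column to the dose table and state a maximum volume rate.

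The cost is an amendment to the protocol and pharmacy wording, plus the stability and compatibility checks. Those checks could delay cohort 3, so they should start now. Cohorts 1 and 2 are not held up.
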